8.11 Treatment Compliance

Compliance with study drug will be monitored and recorded by study personnel based on information from the treating principal investigator and subjects.

8.12 Concomitant Therapy

All subjects will be continued on all their current medications for their medical conditions {except medications listed in item 6.3 that can potentially affect the course and/or management of RLS}.

- **8.13** Recording Concomitant Medication: Medication reconcilliation will be performed by study support staff/personnel and confirmed by investigator during each clinic visit
- **8.14** Extension Study: Not Applicable

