managed clinically by physicians. If deemed appropriate for reasons related to safety, tolerability, and continuation of the study, the PI at his discretion may modify the tapering schedule of the DA although every attempt will be made to adhere to the protocol specified schedule of DA tapering. All subjects will continue to be on Horizant for the entire duration of this study with close follow up.

During each clinic visit all subjects will undergo careful evaluations (by a physician) that will include: medical history such as appearance of any new health problems, any new symptoms/adverse events between clinic visits, concomitant medication(s) history(medication reconciliation), physical examination with assessment of vital signs, ASRS, IRLS, RLS-QOL, and MOS-SS.

All subjects will undergo laboratory testing (CBC with Diff and CMP) during screening, on day 30 and day 360 (final clinic visit). In addition, urine sample will be collected at screen visit for illegal drug testing. Additional hematology and urine sample analysis for illegal drug will be performed as needed at the discretion of the investigators if an adverse event is reported by a subject. Serum Ferritin level will be performed as needed at the discretion of the investigators.

Urine pregnancy screening is required for all females of childbearing potential at screen and each clinical visits, if positive, serum pregnancy test will be performed. Female subjects who have undergone surgical sterilization, who are post-menopausal (defined as age >50 and >1 year of amenorrhea), who have medically documented ovarian failure (defined as age <50 with serum estradiol and follicle-stimulating hormone [FSH] levels within the institutional postmenopausal range and a negative serum or urine β HCG) do not need to undergo pregnancy screening.

Study Procedure

If you agree to be in this study, you will sign this form before any study tests are done. Talk with your study doctor before starting any new medicine. This includes medicines you buy at the drug store and herbal or dietary supplements (vitamins). Some drugs, as well as alcohol, use can cause serious side effects if taken with the study drug. Please ask your study doctor if you have any questions about the medicine(s) you are taking. He/she will tell you which medicine you cannot take during the study.

This study has four periods: screening, treatment and maintenance and follow-up.

Visit 1: Screening Period, (prior to treatment with study drug)

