Blood sample collection: a blood sample (2 teaspoon or \sim 10ml) will be collected for complete blood count with differential and comprehensive metabolic panel at screening visit, visit 3 (day 30) and visit 7 (Day 360). In addition, it will be performed as needed at the discretion of the investigators if an adverse events is reported by a subjects. In other words, if a side effect occurs and the investigator feels additional tests will be helpful, then it will be done. Additional blood sample (\sim 1/4 of teaspoon or 1.25ml) will also be collected if urine pregnancy test turn positive. Serum Ferritin level will be performed as needed at the discretion of the investigators. The total amount of blood sample collected will be 6-7 teaspoon or 30-35ml for the entire study.

7. STUDY POPULATION:

7.1 Number of Subjects: 50 (we believe that we will be able to recruit only 50 eligible subjects during the one year enrollment period)

7.2 Inclusion Criteria:

To be eligible for entry into this study, candidates must meet **all** of the following eligibility criteria before enrollment:

- 1. Adult patients with diagnosis of RLS for more than one year.
- 2. Patients who are on DA therapy for 6 months or longer.
- 3. Patients who developed Augmentation (on stable dose of DA) lasting for 3 months or longer.
- 4. Augmentation severity rating scale of 5 to 15.
- 5. Both males and females
- 6. Age range = 18-85 year

7.3 Exclusion Criteria:

Candidates will be excluded from study entry if **any** of the following exclusion criteria exist at the time of screening phase.

Patients who have history of:

- Known Hypersensitivity to Horizant or Gabapentin products
- o Peripheral neuropathy
- o Radiculopathy
- o Peripheral vascular disease
- o Uremia (abnormal BUN or Creatinine on CMP)
- o Anemia
- o Patients who are currently pregnant
- Patients who currently take opioids, lithium, anti-nausea medications (e.g. metoclopramide), dopaminergic antagonists (e.g. Haloperidol), 1st generation antihistamines (e.g. diphenhydramine, pseudoephedrine), anti-psychotic medications and iron therapy.
- o Subjects with impaired decision making capability.
- 7.4 Medical History Exclusions: as per Exclusion criteria
- **7.5 Treatment History Inclusions or Exclusions**: as per Inclusion and Exclusion criteria
- **7.6 Miscellaneous :** Not applicable
- 7.7 Screening Log: will be maintained

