8.9 Discontinuation of Subjects from Investigational Treatment or from the Study

Subjects must be withdrawn from the study for the following reasons:

- 1. If a subject develops significant adverse effect(s) after addition of Horizant or subject experiences significant DA withdrawal side effects as judge by the investigator.
- 2. If a subject is diagnosed to have a new medical condition while participating in the study that would fall into exclusion criteria (6.3) or if management of a newly diagnosed acute medical problem requires termination of the study medication.
- 3. If a subject becomes pregnant.
- 4. If a subject is deceased.
- 5. XenoPort Inc. may terminate this study, after consultation with investigators, at any time.

8.10 Discontinuation of Study Drug:

The reasons for discontinuation of the study drug must be recorded in the subject's case report form (CRF).

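### Section 8.12 keeps a gabapentin user on gabapentin when gabapentin enacarbil is added, and nothing expressly bars starting gabapentin products, opioids or iron after entry

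*Protocol*

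**What the plan says.** The study drug is Horizant, which is gabapentin enacarbil, 600 mg once daily (Protocol 4 and 8.1).

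- **Concomitant medicines (8.12).** The rule is "All subjects will be continued on all their current medications for their medical conditions". One carve-out follows, in these terms: "except medications listed in item 6.3 that can potentially affect the course and/or management of RLS". There is no item 6.3 on exclusions; the list is in 7.3.
- **Exclusions (7.3).** Candidates are excluded if any "of the following exclusion criteria exist at the time of screening phase". Gabapentin appears once: "Known Hypersensitivity to Horizant or Gabapentin products". The medication entry begins "Patients who currently take opioids, lithium, anti-nausea medications (e.g. metoclopramide" and goes on to dopamine antagonists, first-generation antihistamines, antipsychotics and iron. No gabapentin product is on it.
- **Withdrawal (8.9).** There are five reasons: significant adverse or dopamine-withdrawal effects, a new medical condition, pregnancy, death, and termination by the company. The second concerns a "new medical condition while participating in the study that would fall into exclusion criteria (6.3").
- **Management on study (4 and 6.1).** Worsening RLS after Day 90 is left to the physicians' clinical management, and "the PI at his discretion may modify the tapering schedule of the DA". The Summary also says that subjects in Phase 2 will be on Horizant monotherapy.
- **Advice to subjects (Study Procedure, under 6.1).** Subjects are told to consult the study doctor ahead of any new medicine, and "He/she will tell you which medicine you cannot take during the study". No medicine is named.
- **Recording (8.13 and 9.3).** Medicines are reconciled at every visit.

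**The concern.** A study of a gabapentin product needs a rule on other gabapentin products. This protocol has a rule on concomitant medicines, but as worded it points the wrong way: it continues such a product instead of stopping it. The exception in 8.12 is meant for medicines that can influence RLS or its management. The Protocol presents Horizant itself as an approved RLS treatment (4 and 5.1), so non-study use of it, or of gabapentin, belongs on the list by the Protocol's own reasoning.

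Two things are at stake. The first is tolerability: 10.2 judges Horizant by treatment-emergent events, laboratory changes and examination findings, and in a subject taking a second gabapentin product these reflect combined exposure. The second is attribution. The secondary objective concerns Horizant alone with the dopaminergic agent tapered. If a subject who worsens after Day 90 is given gabapentin, an opioid or iron, a later fall in ASRS or IRLS belongs partly to that medicine. A single-arm study has no comparison group in which the same medicine use would show up.

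**Working it through.** No figure in the Protocol bears on this point, so the check is mainly a reading of the rules against two cases.

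**Case A: a subject already taking gabapentin at screening.**
1. 7.2 asks for an RLS diagnosis, dopaminergic therapy, augmentation, an ASRS of 5 to 15 and age 18 to 85. Gabapentin use affects none of these.
2. 7.3 excludes hypersensitivity to gabapentin products, and current use of seven named kinds of medicine. Gabapentin is not among the seven, so the subject is eligible.
3. 8.12 continues current medicines unless they are on the list, so gabapentin continues.
4. From Day 0, gabapentin enacarbil 600 mg is added.

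The result is two gabapentin products together, reached by following the text. A person already taking prescribed Horizant passes the same steps.

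**Case B: a medicine started or increased after entry.**
1. 7.3 is tied to the screening phase, so it does not act later.
2. None of the five reasons in 8.9 is triggered by starting a medicine. The second needs a new condition.
3. The stable-dose wording (4, 6.1, 7.2) concerns the dopaminergic agent only. 8.7 concerns the scheduled Horizant dose only.
4. 8.12 speaks of current medicines and is silent on new ones.
5. 8.13 and 9.3 record new medicines but restrict none.

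This holds for a gabapentin product and equally for opioids and iron, which 7.3 treats as disqualifying at entry. The on-study gap is therefore general.

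**Which scores could be affected.** Post-baseline scores are taken on Days 30, 90, 120, 180 and 360, which is 5 sets. A start after the Day 90 visit can touch Days 120, 180 and 360, which is 3 of the 5, and leaves the Day 90 comparison alone. A start during Phase 1 could touch Day 90, and the monotherapy wording does not apply in that phase.

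**Size.** If k subjects start such a medicine, each score moves by d points as a result, and n subjects contribute scores, the mean moves by k × d / n. With n = 50, one affected subject moves the mean by d / 50 = 0.02 d. The documents give neither k nor d, and n in Phase 2 will be below 50 if subjects are withdrawn under 8.9. The formula shows how the effect scales; it does not yield an estimate.

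**The case against.** The strongest reply is that the protocol does more than its lists suggest.

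- **Phase 2 is described as Horizant monotherapy.** A subject given gabapentin for worsening RLS is no longer on it. This bears directly on the most plausible route, a start after Day 90. It stands in part: it states the intended regimen, but it prohibits no medicine, does not clearly reach gabapentin taken for another condition, and does not cover Phase 1.
- **Subjects must speak to the study doctor first.** This is a check before a new medicine is started, and disallowed medicines are to be stopped at screening. It stands as a safeguard, but no medicine is named, and the only list the doctor could work from is 7.3.
- **Other outlets exist.** The taper can be changed, and significant dopamine-withdrawal effects require withdrawal. Both make an added medicine less likely.
- **Few gabapentin users may be eligible.** 7.3 excludes peripheral neuropathy and radiculopathy, which may remove some. That is plausible but indirect.
- **How scores are counted belongs to the analysis plan.** This is fair for the detail. Eligibility and permitted medicines are protocol content, and this protocol fixes both.

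A reader might go further and infer that background gabapentin biases the efficacy result. The documents do not support that. The outcomes are reductions or improvements in scores, and a stable background dose is present at baseline and at follow-up alike. Nor do they support saying that the protocol authorises gabapentin as rescue; it fails to bar it, which is less. Finally, the wrong reference to 6.3 does not leave the study without an exclusion list. There is only one such list, so the slip is editorial.

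**Conclusion.** The point holds in a limited form and is minor. At entry, 8.12 and 7.3 together produce a badly fixed rule: current gabapentin continues alongside gabapentin enacarbil, and tolerability of Horizant 600 mg is confounded in any such subject. This follows from the text and needs no assumption except that at least one such subject enrols, which the documents do not tell us.

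On study, no provision expressly bars starting or increasing a gabapentin product, or starting a medicine that 7.3 lists. Any resulting change could be credited to Horizant in a study with no control. The monotherapy wording and the advice to consult the study doctor reduce that risk without removing it.

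The effect on mean scores cannot be derived from the documents and may be zero. Nothing shows that the primary Day 90 comparison is compromised: a start after Day 90 cannot affect it, and a start before then is possible but not shown to be likely.

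**What to change.** 1. In 7.3, add current use of gabapentin, or of gabapentin enacarbil from outside the study, to the excluded medicines.
2. In 8.12, state that these products and the other medicines listed in 7.3 may not be started or increased from screening through Day 360. Add that Phase 2 scores after any such start or increase are not counted as Horizant monotherapy. Identify them from the existing medication reconciliation, and report how many subjects are affected, so that setting aside scores from subjects who worsened does not flatter the result.
3. As an editorial correction, change 6.3 to 7.3 in 8.9 and 8.12.

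The cost is one line, a short addition and two corrected references. No new data are needed, because medicines are already reconciled at each visit. The one real drawback is possibly a few fewer eligible subjects at a site that expects to recruit only 50.

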9. SCHEDULE OF EVENTS

9.1 **Laboratory Tests:** All subjects will undergo laboratory tests (CBC with Diff and CMP) during screening phase, on day 30 and day 360 (final clinic visit). In addition, urine sample will be collected at screen visit for illegal drug screen. Additional urine illegal drug screen and hematology analysis will be performed as needed at the discretion of the investigators if an adverse event is reported by a subject. Serum Ferritin level will be performed as needed at the discretion of the investigators.

Urine pregnancy screening is required for all females of childbearing potential at screen and each clinical visits, if positive, serum pregnancy test will be performed. Female subjects who have undergone surgical sterilization, who are post-menopausal (defined as age >50 and >1 year of amenorrhea), who have medically documented ovarian failure (defined as age <50 with serum estradiol and follicle-stimulating hormone [FSH] levels within the institutional postmenopausal range and a negative serum or urine β HCG) do not need to undergo pregnancy screening.

9.2 Study Site Personnel and Responsibilities:

Where specified, evaluations described in this section must be performed only by the personnel indicated.

9.2.1 **The Independent Assessment Panel or Centralized Reading/Evaluating Group:** not applicable

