3 STUDY FLOW CHART

	Pre-Rx 'Screening Phase' (duration	Baseline	Rx Phase 1		Rx Phase 2		
	= 15 days)	Day 0 +/-7	Day 30 +/-7	Day 90 +/-14	Day 120 +/-14	Day 180 +/-14	Day 360 +/-14
Enrolment Period	1 year						
Medical History**	X	X	X	X	X	X	X
Concomitant Medication(s)	X	X	X	X	X	X	X
Vital Signs	X	X	X	X	X	X	X
Physical Examination	X	X	X	X	X	X	X
ASRS(*)	X	X	X	X	X	X	X
IRLS(*)	X	X	X	X	X	X	X
RLS-QOL(*)		X	X	X	X	X	X
MOS-SS(+*)		X	X	X	X	X	X
CBC and differential, CMP	X		X				X
Monitoring & Recording of Adverse Events		X	X	X	X	X	X
Urine pregnancy analysis	X	X	X	X	X	X	X
Urine sample collection (drug screen)	X						
Serum pregnancy analysis Serum Ferritin Level	TBD	TBD	TBD	TBD	TBD	TBD	TBD

Rx Phase 1 (Day 0-90) = Stable DA + Horizant

Rx Phase 2 (Day 120-360) = DA taper/Horizant only

- + = Subjects will also be requested to keep a sleep diary.
- * = See attachments.
- ** = Medical history includes Interval history between clinic visits.

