Abrupt withdrawal of DA agent can be potentially dangerous due to DA withdrawal symptoms including life-threatening Neuroleptic Malignant Syndrome. Therefore, Rx Phase 1 and Rx Phase are designed to help improve subject tolerability.

Therefore, during Rx Phase 1, Horizant (600 mg oral once daily at 5 pm) will be added on as an adjunct to all subjects' along with stable dose of their current dopaminergic (DA) agent and both medications will be continued for a total period of 90 days from day 0 to day 90.

At the 90th day follow-up visit, with initiation of Rx Phase 2, all subjects will be tapered off (by 50% reduction in dose each week) of their current dopaminergic agent while maintaining the same dose of Horizant and will be on Horizant monotherapy. All subjects will be followed for additional three follow up clinic visits (days 120, 180, 360).

During this period all subjects will be monitored for symptoms of dopamine withdrawal or worsening of RLS or emergence of other symptoms which will be managed clinically by physicians. All subjects will continue to be on Horizant for the entire duration of this study with close follow up. Of note, if deemed appropriate for reasons related to safety, tolerability, and continuation of the study, the PI, at his discretion, may modify the tapering schedule of the DA although every attempt will be made to adhere to the protocol specified schedule of DA tapering.

During each clinic visit all subjects will undergo careful evaluations (by a physician) that will include: medical history such as appearance of any new health problems, any new symptoms/adverse events between clinic visits, concomitant medication(s) history (medication reconciliation), physical examination with assessment of vital signs, ASRS, IRLS, RLS-QOL, and MOS-SS.

All subjects will undergo laboratory testing (CBC with Diff and CMP) during screening, on day 30 and day 360 (final clinic visit). In addition, urine sample will be collected at screen visit for illegal drug testing. Additional hematology and urine sample analysis for illegal drug will be performed as needed at the discretion of the investigators if an adverse event is reported by a subject. Serum Ferritin level will be performed as needed at the discretion of the investigators.

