- We will instruct you on how to discontinue any medications not allowed while you are in the study. Without your regular medications, your medical conditions or symptoms may get worse however, we will check with the doctor that prescribed the medication to make sure that it is safe for you to stop taking it. You might not be able to drive or operate machinery. If your medical conditions or symptoms do get worse, please call the study doctor at the phone number provided in this consent form.
- We will make an appointment for you to return for Visit 2 (baseline visit), within the next 15 days or less.

Visit 2 (day 0+/-7), visit 3 (day 30+/-7), visit 4 (day 90+/-14), visit 5 (day 120+/-14), visit 6 (day 180+/-14) and visit 7 (day 360+/-14) will have the following tests and procedures except that visit 2, 4, 5 and 6 will not have blood sample collection.

- Medical history: We will ask about your health and any illnesses and any changes in medicines you are taking or have taken since last visit.
- We will ask you about your current and prior Augmentation treatment, symptoms, your usual bedtime and awakening times.
- You and the staff will complete assessments on how you are feeling and if you have any thoughts about harming yourself.
- Physical examination: You will have a full physical examination including neurological exam, height and weight.

- Vital signs: You will have your temperature, heart rate, blood pressure, temperature and breathing rate collected.
- Blood testing: We will collect blood samples (2 teaspoon or~10ml) for lab tests including hematology. Additional blood sample (~1/4 of teaspoon or 1.25ml) will be collected if you are a woman and your urine pregnancy test turn positive.
- Urine testing: You will collect a sample of urine for pregnancy testing.
- Augmentation severity rating scale (ASRS) 3 item questionnaire to evaluate the severity of your augmentation symptom.
- International restless legs syndrome-rating scale (IRLS) a way to measure severity of your symptoms.
- Restless legs syndrome-quality of life (RLS-QOL) a way to measure improvement in quality of your life.
- Medical outcome study-sleep scale (MOS-SS) a way to assess your sleep.

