11.1.2 Serious Adverse Events

In accordance with 21 Code of Federal Regulations (CFR) Part 312.32 and the recommendations of the International Conference on Harmonization (ICH) [Federal Register, October 7, 1997, Vol. 62, No. 194, pp 52239-45], any of the following adverse events are to be classified as a serious adverse event (SAE):

- An event that results in death.
 - An event that, in the view of the Investigator, places the subject at immediate risk of death (a life-threatening event). This does not include an event that, had it occurred in a more severe form, might have caused death.
 - An outcome that results in a congenital anomaly/birth defect diagnosed in a child of a subject who participated in this study.
 - An event that requires or prolongs in-patient hospitalization.
 - An event that results in persistent or significant disability/incapacity.
 - Other medically important events that, in the opinion of the Investigator, may jeopardize the subject or may require intervention to prevent one of the other outcomes listed in the definition above. (Examples of such medical events include allergic bronchospasm requiring intensive treatment in an emergency room or convulsions occurring at home that do not require an in-patient hospitalization.).

If a serious adverse event is unresolved when a subject permanently discontinues the study, the subject will be followed until the event resolves or the clinical course is stabilized.

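### No CBC/CMP is required at early withdrawal, so after the Day 30 draw the laboratory safety record rests on completers plus discretionary tests

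*Protocol*

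**What the plan says.** Section 9.1 fixes the laboratory schedule: "All subjects will undergo laboratory tests (CBC with Diff and CMP) during screening phase, on day 30 and day 360 (final clinic visit". The flow chart in section 3 marks the row "CBC and differential, CMP" at screening, Day 30 and Day 360 and has no early-withdrawal column. The visit list under Study Procedure in section 6.1 confirms this by giving Visits 2 to 7 the same tests, "except that visit 2, 4, 5 and 6 will not have blood sample collection". Those four visits are Days 0, 90, 120 and 180.

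Section 8.9, item 1, requires withdrawal in this case: "If a subject develops significant adverse effect(s) after addition of Horizant or subject experiences significant DA withdrawal side effects", as judged by the investigator. Section 8.10 adds one documentation duty, "The reasons for discontinuation of the study drug must be recorded", in the case report form. Neither section attaches a visit or a blood sample. Section 11.1.2 provides that "If a serious adverse event is unresolved when a subject permanently discontinues the study, the subject will be followed until the event resolves" or stabilises, without naming a laboratory test.

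Unscheduled testing is allowed. The blood-sample paragraph of Study Procedure covers CBC and CMP: "if a side effect occurs and the investigator feels additional tests will be helpful, then it will be done". Sections 4, 6.1 (Study Design) and 9.1 name only hematology as the additional blood test after an adverse event. Section 10.2 allows further labs generally, at the investigator's discretion, and lists laboratory changes of clinical significance as one of its three safety and tolerability measures.

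**The concern.** Laboratory change is a declared safety measure, but the scheduled samples that inform it after Day 30 come only from subjects who reach Day 360. Subjects taken out because treatment or the taper harmed them contribute a later value only if someone chose to order a test. Whether such a value exists then varies with the clinician and the event, not with the plan. The trial is single-arm with 50 subjects, so no control group helps a reader to judge what the missing values might have shown.

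The gap also covers Phase 2. Section 4 says: "At the 90th day follow-up visit, with initiation of Rx Phase 2, all subjects will be tapered off". A subject withdrawn during or after the taper and before Day 360 has no scheduled laboratory value from that phase. The timing of blood draws belongs in the protocol, and no later analysis plan can recover a sample that was not taken.

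**Working it through.** **Inputs.**
- Scheduled CBC/CMP: screening, Day 30, Day 360 (sections 3, 4, 6.1, 9.1).
- Visit window at Day 30: plus or minus 7 days (section 3 and the visit list in 6.1).
- Volume per draw: about 10 ml. Stated study total: 30-35 ml (section 6.1, blood-sample paragraph).
- Sample size: 50 (section 7.1).
- Withdrawal rate: not given.

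**Step 1. Check the schedule against the stated blood volume.** 3 draws x 10 ml = 30 ml, the lower end of 30-35 ml. The remaining 0-5 ml leaves room for conditional samples, such as the 1.25 ml serum pregnancy test. The stated total therefore agrees with three scheduled draws and no routine fourth, which would give 4 x 10 = 40 ml.

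**Step 2. Locate the cut-off.** The dividing point is the actual Day 30 draw: 30 - 7 = Day 23 to 30 + 7 = Day 37.

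**Step 3. Count scheduled on-treatment values and scheduled volume, now and with an exit sample.**

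| Subject | On-treatment values now | With exit sample | Volume now | With exit sample |
|---|---|---|---|---|
| Withdrawn before the Day 30 draw | 0 | 1 | 10 ml | 20 ml |
| Withdrawn after it, before Day 360 | 1 | 2 | 20 ml | 30 ml |
| Completer | 2 | 2 | 30 ml | 30 ml |

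The counts with an exit sample are maxima, since a subject who has died or who declines gives none. The volume never exceeds that of a completer.

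**Step 4. Number of subjects affected.** This cannot be derived from the protocol. Purely as an assumption, withdrawal of 10%, 20% or 30% before Day 360 would leave 0.10 x 50 = 5, 0.20 x 50 = 10 or 0.30 x 50 = 15 subjects without a scheduled final value. These figures count withdrawal for any reason, not only for harm under section 8.9, item 1.

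**Step 5. Does another provision require the missing sample?**
- Section 9.1 labels Day 360 as the final clinic visit. That could be taken to mean each subject's own last visit, but the flow chart ties the draw to the Day 360 column and the visit list rules out blood at Days 0, 90, 120 and 180.
- Section 8.10 asks for a reason, not a test.
- Section 11.1.2 requires follow-up of unresolved serious events only, and names no test.
- The as-needed provisions permit a test if the investigator thinks it useful.

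None of these makes an exit CBC/CMP mandatory.

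**The case against.** The schedule is internally consistent, and event-triggered testing is a legitimate design. A subject withdrawn under section 8.9, item 1, has by definition a significant adverse or withdrawal effect, which is the situation in which section 6.1 allows an extra CBC/CMP and section 10.2 allows labs as needed. Serious events are pursued to resolution or stabilisation. Adverse events and new complaints, the other section 10.2 measures, are collected at every visit from baseline. The laboratory measure carries no hypothesis, threshold or stopping rule in the protocol, and the stated outcomes are four clinical scales.

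Much of this stands, and it limits the weight of the point. It does not remove it, because permission is not a requirement. The as-needed wording is also uneven: a site working from section 9.1 is pointed to hematology, not to a CMP.

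Three stronger readings are tempting but unsupported:
- A reader might infer that withdrawn subjects cannot have a late test. They can; it is simply not scheduled.
- A reader might infer that withdrawn subjects are the likeliest to show abnormal blood counts or chemistry. That is plausible, but nothing in the protocol links Horizant's effects or dopaminergic withdrawal to CBC or CMP changes.
- A reader might take the 330 days between the two on-treatment draws (360 - 30) as the size of the defect. That interval applies to every completer and an exit sample does not shorten it, so it describes sparse sampling in general and not this gap.

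**Conclusion.** The point holds for scheduled values. Followed exactly, the plan yields 0 scheduled on-treatment CBC/CMP values for a subject withdrawn before the Day 30 draw, 1 for a subject withdrawn between that draw and Day 360, and 2 for a completer. After Day 30, the laboratory component of the section 10.2 assessment rests on completers and on tests that investigators chose to order. How many of the 50 subjects this touches is unknown.

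It is a minor weakness in the safety data that is cheap to repair. The efficacy conclusions are unaffected, and the trial remains interpretable without the change. The conclusion assumes that Day 360 means the calendar visit and not each subject's last visit; if the sponsor intends the latter, the edit below only makes that explicit.

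**What to change.** In section 9.1, and in the matching text of sections 4, 6.1 (Study Design) and 6.1 (Study Procedure, blood-sample paragraph), write:

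> The final CBC with differential and CMP is taken at Day 360 or, for a subject withdrawn earlier, at withdrawal, if the subject is able and willing. An as-needed CBC/CMP taken at withdrawal counts as this sample.

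Three conforming edits are needed so that the change does not create a contradiction:
- Mark the withdrawal sample in the section 3 flow chart, as a footnote or an added column.
- State the same requirement in sections 8.9 and 8.10.
- In the section 6.1 visit list, qualify the statement that Visits 2, 4, 5 and 6 have no blood sample with: *except when the visit is the subject's withdrawal visit*.

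**Cost.** A withdrawn subject gives one draw of about 10 ml at withdrawal in place of the Day 360 draw. Completers give nothing extra, and the scheduled total stays at 30 ml or less. Under section 14.3 the amendment goes to the company first and then to the IRB, with matching consent wording. The sample depends on the subject's ability and willingness, so it will reduce the gap without fully closing it.
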